4.10.2.5 Main Analysis

For the analysis of the primary efficacy variables, an ANCOVA will be used, with the questionnaire score at baseline as a covariate and the treatment arm as fixed factor.

The above-mentioned ICEs except for death are expected. Occurrences of missing data will generally be assumed at random and therefore missingness handled by case-exclusion for each ANCOVA, meaning only pairs of available baseline and post-baseline assessments will be analyzed. The case of missingness due to treatment-related AE will be investigated in Sensitivity Analysis 2.

Only in case of death missing data will be imputed using the composite strategy using the worst possible outcome (i.e. maximum score of 120 for the BIS-11 questionnaire and 80 for the S-UPPS-P Impulsive Behavior Scale questionnaire) for patients who die in between baseline assessment and Day 14 assessment.

In the example of the change from baseline in total score of BIS-11 at steady state (at Day 14), the observation at Day 14 of patient i receiving treatment t can be written as follows:

$$Y_{it} = \beta_0 + \mu_t + x_i \beta_{base} + \epsilon_{it}$$

with

[figure not shown]
- Y_{it} being the change from baseline to Day 14 for the ith patient,
- β_0 being the intercept,
- μ_t being the treatment effect,
- x_i being the baseline BIS-11 questionnaire score of patient i,
- β_{base} the fixed effect of the baseline BIS-11 questionnaire score,
- ϵ_{it} the residual error with $\epsilon_{it} \sim N(0, \sigma_t^2)$ being the residual error for treatment arm t.

In terms of the model parameters, the estimate of the population-level summary of the estimand (i.e. the treatment effect at Day 14) can then be expressed as

$$\widehat{diff}_{treat} = \widehat{\mu}_t^{(Atomoxetine)} - \widehat{\mu}_t^{(Placebo)}.$$

Summary tables will include number of patients, LSmean)change, (unadjusted) mean change and SD and baseline means of each treatment group and the estimate of the treatment difference expressed as LSmean difference including the corresponding two-sided 95% confidence interval. Each ANCOVA will be accompanied by a residual plot showing the predicted value versus the

standardized residual. SAS html outputs for each ANCOVA procedure will be stored as statistical output appendix.

4.10.3 Secondary Endpoints

Please refer to Section [4.11.1 Adverse Events](#).

 **CONFIDENTIAL**

Project Document Version No. 2.0

Effective Date: 30 Jan 19

Project Document Effective Date: Date of last signature

[figure not shown]
Related to: 

Page 28 of 41

Boehringer Ingelheim

2021-005270-26

Statistical Analysis Plan

CONFIDENTIAL

Project Document Version No. 2.0

Effective Date: 30 Jan 19

Project Document Effective Date: Date of last signature

[figure not shown]
Related to: [REDACTED]

Page 29 of 41

Boehringer Ingelheim

2021-005270-26

Statistical Analysis Plan

CONFIDENTIAL

Project Document Version No. 2.0

Effective Date: 30 Jan 19

Project Document Effective Date: Date of last signature

[figure not shown]
Related to: [REDACTED]

Page 30 of 41

Boehringer Ingelheim

2021-005270-26

Statistical Analysis Plan

 **CONFIDENTIAL**

Project Document Version No. 2.0

Effective Date: 30 Jan 19

Project Document Effective Date: Date of last signature

Related to: 

Page 31 of 41

Boehringer Ingelheim

2021-005270-26

Statistical Analysis Plan

CONFIDENTIAL

Project Document Version No. 2.0

Effective Date: 30 Jan 19

Project Document Effective Date: Date of last signature

[figure not shown]
Related to: [REDACTED]

Page 32 of 41

Boehringer Ingelheim

2021-005270-26

Statistical Analysis Plan

CONFIDENTIAL

[figure not shown]
Project Document Version No. 2.0

Effective Date: 30 Jan 19

Project Document Effective Date: Date of last signature

Related to: [REDACTED]

Page 33 of 41

4.10.5 Pharmacokinetics

4.10.5.1 Pharmacokinetic Concentrations

All collected pharmacokinetic concentrations of atomoxetine will be listed for each participant and by treatment (at least the Placebo samples for the timepoints Visit 3, Planned Time 2:00 hours and Visit 4, 314:00 hours will be measured) in the TS. Listings will include actual sampling times relative to dose administration, the subject's inclusion in the PK-PPS and concentrations' inclusion/exclusion from the analysis with the reason for exclusion. Plasma concentrations below the LLOQ will be presented as BLQ in the listings.

Plasma concentration data of a patient will be included in the PK analyses (i.e. descriptive summaries), if they are not flagged for exclusion due to a protocol deviation relevant to the evaluation of PK (in a Data Review Meeting prior to database lock) or due to PK non-evaluability (as revealed during data analysis, based on the criteria specified below). Only concentrations within the validated concentration range will be used. Handling of pharmacokinetic concentrations will be done according to BI standards. Exclusion of a patient's data will be documented in the Clinical Trial Report and excluded data listed together with the reason for exclusion.

Reasons for data exclusions considered include, but are not limited to:

- Vomiting occurs on Day 1 or 14 post-dose, but prior to or during a PK sampling and will be finally confirmed during AE review (see Section 4.10.1.6)
- PK samples are collected more than 30 minutes before the nominal time of 2:00 hours after study drug administration (start time of impulsivity testing), and / or more than 30 minutes after the nominal time of 3:00 hours after study drug administration (end of impulsivity testing) after study drug administration on Day 1 and 14 and will be confirmed during PK data review
- No study drug intake on Day 1 or 14

CONFIDENTIAL

Project Document Version No. 2.0

Effective Date: 30 Jan 19

Project Document Effective Date: Date of last signature

Related to: [REDACTED]

[figure not shown]
Page 34 of 41

Plasma concentrations of atomoxetine will be summarized by treatment group, visit and nominal timepoint. The following descriptive statistics will be presented for plasma concentrations obtained at each nominal time point: n, arithmetic mean, SD, arithmetic coefficient of variation (CV%), geometric mean, geometric CV%, geometric SD, median, minimum, maximum and percentiles 10, 25 (1st quartile), 75 (3rd quartile) and 90.

The geometric mean / SD will be calculated as the exponential value of the arithmetic mean / SD of natural logarithm transformed concentrations. The geometric CV% will be calculated as $gCV\% = \text{SQRT}(e^{s^2}-1)*100$; where s is the standard deviation of the log-transformed values.

The following rules will be followed with regards to the number of decimal places and presentation of data in the tables and listings of concentration data:

- Source data shall be used in all derived PK concentrations without prior rounding.
- Statistics resulting from computations (mean, SD, geometric mean, geometric SD, median and percentiles) will be tabulated to one more digit compared to the source data, but with a maximum of four significant digits.
- Minimum and maximum values will be tabulated to the same precision as the source data, but with a maximum of four significant digits.
- Geometric coefficient of variation (CV) % and coefficient of variation (CV%) will be presented to one decimal place.

4.10.5.2 Handling of Values Below the Limit of Quantification

Concentrations identified as Below the Limit of Quantification (BLQ) will be substituted by LLOQ/2 for calculations.

All concentrations BLQ will be labeled as such in the concentration data listings. Missing samples will be reported as no sample ("NOS") and excluded from analysis. Summary statistics

will only be calculated if the number of available, non-BLQ values is ≥ 3 . If this number is < 3 , only the n, minimum and maximum will be presented.

4.10.5.3 Pharmacokinetic Parameters

No pharmacokinetic parameters will be calculated. Only plasma concentrations and descriptive statistics of plasma concentrations will be reported.

4.11 Safety Evaluation

All safety listings, summaries and analyses will be based upon the TS as defined in Section 4.5.

4.11.1 Adverse Events

- An AE is defined as any untoward medical occurrence in a patient or clinical investigation subject administered a medicinal product and which does not necessarily have to have a causal relationship with this treatment.

An AE can therefore be any unfavourable and unintended sign (including an abnormal laboratory finding), symptom, or disease temporally associated with the use of a medicinal product, whether considered related or not.

The following should also be recorded as an AE in the CRF and Boehringer Ingelheim SAE form (if applicable):

- Worsening of the underlying disease or of other pre-existing conditions.
- Changes in vital signs (body temperature, systolic and diastolic blood pressure, and pulse rate), ECG, physical examination (QTc interval and interpretation, clinically relevant abnormal findings), assessment of suicidality via C-SSRS and laboratory test results (hematology, chemistry, enzymes, electrolytes, substrates, pregnancy test, urinalysis [at screening]), if they are judged clinically relevant by the investigator.
- If such abnormalities already exist prior to trial inclusion, they will be considered as baseline conditions and should be collected in the eCRF only.
- A TEAE is defined as an AE that begins or that worsens in severity after at least one dose of the study drug has been administered. Only AEs with start date until 4 days after the last dose of study drug are considered as TEAEs.
- An SAE is defined as any AE, which fulfils at least one of the following criteria:
 - results in death,
 - is life-threatening, which refers to an event in which the patient was at risk of death at the time of the event; it does not refer to an event that hypothetically might have caused death if more severe,
 - requires inpatient hospitalisation or prolongation of existing hospitalisation

CONFIDENTIAL

Project Document Version No. 2.0

Effective Date: 30 Jan 19

Project Document Effective Date: Date of last signature

Related to: [REDACTED]

Page 36 of 41

- results in persistent or significant disability or incapacity,
- is a congenital anomaly / birth defect,
- is deemed serious for any other reason if it is an important medical event when based on appropriate medical judgement which may jeopardise the patient and may require medical or surgical intervention to prevent one of the other outcomes listed in the above definitions. Examples of such events are intensive treatment in an emergency room or at home for allergic bronchospasm, blood dyscrasias or convulsions that do not result in hospitalisation or development of dependency or abuse.
- Adverse events will be coded using the MedDRA Version 24.1 or higher.
- Listings and tables showing AEs will be based on the TS.
- Where dates are missing or partially missing, AEs will be assumed to be treatment-emergent, unless there is clear evidence (through comparison of partial dates) to suggest that the AE started prior to the first dose of study drug.
- Adverse event summaries will be ordered in terms of decreasing frequency for SOC, and PT within SOC, in the study drug treatment group, and then alphabetically for SOC, and PT within SOC.
- For each subject and each AE, the worst severity recorded will be attributed and used in the by-severity summaries. Similarly, the worst causality (most related to treatment) will be attributed and used in the by-causality summaries. If severity or causality is missing, the worst case will be assumed.

AE information will be listed per subject including the MedDRA SOC, PT and reported term. The listing will include at least age, sex, race of the patient and start/end date/time, relationship to study drug per the investigator's opinion, severity, seriousness, outcome, duration, leading to dropout, action taken of the event.

The following descriptive summaries will be produced for TEAEs with percentages based on the number of subjects in the TS:

- A summary of the number and percentage of subjects reporting a TEAE by seriousness, relationship to study drug, maximum severity, death and leading to discontinuation for each treatment group
- A summary of the number and percentage of subjects reporting a TEAE by treatment group, SOC and PT including the number of events.
- A summary of the number and percentage of subjects reporting an SAE by treatment group, SOC and PT including the number of events.

- A summary of the number and percentage of subjects reporting a TEAE resulting from the C-SSRS assessment 'since last visit' (per the investigator's clinical judgement) by treatment group, seriousness, SOC and PT including the number of events.
- A summary of the number and percentage of subjects reporting treatment-emergent vomiting or nausea by treatment group, SOC and PT including the number of events.
- A summary of the number and percentage of subjects reporting a TEAE that exceed a frequency of 5 percent within any treatment arm by treatment group, SOC and PT including the number of events (i.e. only those events with a PT that occurs in more than 5% of patients of the TS).

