6.2.3 Follow-up period and trial completion

EoS - Visit 5 (day 19 to 28)

All Subjects completed the treatment (or who discontinue treatment before the end of the planned treatment period) should undergo the EoTrial Visit.

Following safety assessments will be performed: C-SSRS, physical exam, ECG, vital signs, safety lab (including urine pregnancy test for WOCBP), assessment of AEs and concomitant therapy.

If needed in the opinion of the investigator, after the EoS (End of Trial) visit additional visits may be scheduled for continued safety monitoring.

Abnormal assessments or lab values judged clinically relevant by the investigator will be monitored until they returned to a medically acceptable level.

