7.2.6 Safety analyses

Adverse events will be coded using the Medical Dictionary for Drug Regulatory Activities (MedDRA). Standard BI summary tables and listings will be produced. All adverse events with an onset between start of treatment and end of the REP, a period of 4 days the last dose of trial medication, will be assigned to the on-treatment period for evaluation.

All treated patients will be included in the safety analysis. In general, safety analyses will be descriptive in nature and will be based on BI standards. No hypothesis testing is planned.

Statistical analysis and reporting of adverse events will concentrate on treatment-emergent adverse events, i.e. all adverse events occurring between start of treatment and end of the REP. Adverse events that start before first drug intake and deteriorate under treatment will also be considered as 'treatment-emergent'.

Frequency, severity, and causal relationship of adverse events will be tabulated by system organ class and preferred term after coding according to the current version of the Medical Dictionary for Drug Regulatory Activities (MedDRA) at database lock.

Laboratory data will be analysed both quantitatively as well as qualitatively. The latter will be done via comparison of laboratory data to their reference ranges. Values outside the reference range as well as values defined as clinically relevant will be summarised. Treatment groups will be compared descriptively with regard to distribution parameters as well as with regard to frequency and percentage of patients with abnormal values or clinically relevant abnormal values.

Vital signs, physical examinations, or other safety-relevant data observed at screening, baseline, during the course of the trial and at the end-of-trial evaluation will be assessed with regard to possible changes compared to findings before start of treatment.

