4.3.1.3 Dates for AEs

The imputation of missing / incomplete AE onset date/time is performed according to the following steps:

Step 1: For each missing / incomplete AE onset date, an interval (INT_START, INT_END) is defined. The true unknown analysis start date of the AE is assumed to be within this interval.

Scenario of AE onset date	INT_START	INT_END
Completely missing AE onset date	Min(AE end date, Date of informed consent)	Min(AE end date, Date of last visit)
Only year of AE onset date is non-missing	Min(AE end date, 01 JAN of the reported year)	Min(AE end date, 31 DEC of the reported year)
Only year and month of AE onset date are non-missing	Min(AE end date, 01 of the reported month)	Min(AE end date, Last date of the reported month)

Note: Completely missing AE end date will not be considered in this derivation step. Partially missing AE end date (i.e. year and month are non-missing or only year is non-missing) will be temporarily assigned the largest possible date in the observed year or month and year in this derivation step.

Step 2: Derive an imputed AE onset date based on the interval from step 1

Scenarios	On-Study AE / Not On-Study AE	Imputed AE onset date
1. Date of baseline is within the interval [INT_START, INT_END]	On-study	Date of baseline
2. Date of baseline is before INT_START	On-study	INT_START from step 1
3. Date of baseline is after INT_END or missing	Not on-study	INT_END from step 1

Step 3: The AE onset date / time imputation flag(s) are set according to the level of imputation performed and the standard CDISC rules for imputation or the legacy data imputation rules.

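### SAP 4.11.1 sets no end date for the worsening of a pre-dose AE, and its partial-date default conflicts with the SAP's own onset imputation in one class of cases

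*SAP*

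**What the plan says.** Protocol 7.2.6 treats events as treatment-emergent from the start of treatment to the end of the residual effect period (REP), 4 days after the last dose. For events already present it adds: "Adverse events that start before first drug intake and deteriorate under treatment will also be considered as" treatment-emergent.

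SAP 4.11.1 words the rule differently. Its opening definition, quoted here without its last word, reads: "A TEAE is defined as an AE that begins or that worsens in severity after at least one dose of the study drug has been". The sentence that follows it is: "Only AEs with start date until 4 days after the last dose of study drug are considered as TEAEs". The second sentence limits the start date. Nothing limits the date of worsening.

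For incomplete dates, SAP 4.11.1 sets a default: "Where dates are missing or partially missing, AEs will be assumed to be treatment-emergent, unless there is clear evidence (through comparison of partial dates"). The only evidence that lifts it is evidence "to suggest that the AE started prior to the first dose of study drug". SAP 4.3.1.3 separately imputes incomplete onset dates. In the row "Date of baseline is before INT_START" the imputed onset is INT_START. For a month-only date that is the first of the month, or the AE end date if that is earlier.

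The final visit in Protocol 6.2.3 is "EoS - Visit 5 (day 19 to 28"), and Protocol 5.2.6.2.1 collects AEs from consent until that visit. SAP 3.2.2 defines the only secondary endpoint as the percentage of patients with treatment-emergent AEs and SAEs. SAP 4.13 lists no changes from the Protocol.

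**The concern.** The treatment-emergent flag sets the numerator of the only secondary endpoint. If the SAP rule and the Protocol rule classify the same event differently, the reported percentage depends on which document the programmer follows, and the SAP does not acknowledge a departure.

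The situation can arise. Screening may last up to 28 days, AEs are recorded throughout it, and some patients stop restricted medication before baseline (Protocol 6.2.1). AEs can therefore be open at first dose and can worsen again after study drug has stopped.

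The partial-date default has a similar one-sided form: it can be lifted for an onset shown to be too early, but not for one shown to be too late.

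**Working it through.** **Inputs.** Longest half-life 19 h and REP of 4 days (Protocol 1.2); last planned dose on Day 14 (Protocol 4.1.1 and 4.1.4); final visit on Day 19 to 28 (Protocol 6.2.3); 80 evaluable and up to 96 randomised patients at 1:1, so 40 to 48 per arm (Protocol synopsis and 3.3).

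**Step 1: the plan's own figure.** REP = 5 × 19 h = 95 h; 95/24 = 3.96 days, rounded up to 4. The stated REP is reproduced.

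**Step 2: the window for a completer.** REP end = Day 14 + 4 = Day 18. Follow-up beyond it runs from 19 − 18 = 1 day to 28 − 18 = 10 days, depending on the date of the final visit.

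**Step 3: the two rules on fully dated events**, reading the Protocol's treatment period as ending with the REP:

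| Start | Worsens | SAP 4.11.1 | Protocol 7.2.6 |
|---|---|---|---|
| Day −5 | never | no | no |
| Day −5 | Day 10 | yes | yes |
| Day −5 | Day 18 | yes | yes |
| Day −5 | Day 19 | **yes** | **no** |
| Day −5 | Day 28 | **yes** | **no** |
| Day 18 | never | yes | yes |
| Day 19 | never | no | no |

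The rules disagree on each worsening day from 19 to 28, which is 10 days. If the Protocol's deterioration rule is read as ending at the last dose, they disagree from Day 15 to Day 28, which is 14 days. For fully dated events that do not worsen, they agree on every onset day.

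**Step 4: partial dates.** Suppose Day 1 is 10 March, so Day 14 is 23 March, Day 18 is 27 March and 1 April is Day 23. An AE dated only April cannot have begun before Day 23. SAP 4.3.1.3 imputes 1 April, and the start-date limit in 4.11.1 then excludes it. The default in 4.11.1 counts it, because nothing suggests onset before first dose. The two results cannot both be programmed.

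An AE dated only March may have begun inside or outside the window, and no rule can tell which.

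**Step 5: how often the date itself proves late onset.** Assume true onset is equally likely on Days 19 to 28. For onset *k* days past the REP (*k* = 1 to 10), proof requires a month to begin within those *k* days, with probability about *k* × 12/365.25. The average of *k* is 5.5, so the share is 5.5 × 12/365.25 = 0.181. Enumerating every Day 1 date from 2022 to 2025 also gives 0.181. About 18% of month-only follow-up onsets are therefore provably late; in the other 82% the month overlaps the window.

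**Step 6: size per patient.** 1/40 = 2.5 points and 1/48 = 2.1 points, provided the patient has no other treatment-emergent event.

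**The case against.** The strongest reply on worsening concerns recording. Protocol 5.2.6.1.1 and SAP 4.11.1 both say that worsening of the underlying disease or another pre-existing condition is itself recorded as an AE. Such a record has its own start date, and the 4-day limit already excludes it if it falls too late. ADHD worsening after study drug stops may well be handled this way.

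That narrows the point but does not remove it. The SAP does not say that a worsened pre-dose AE becomes a new record. Its worsening clause has a purpose only if the event keeps its pre-dose start date, and the by-severity summaries take the worst severity recorded for each AE. If new-record handling is intended, the SAP should say so.

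On partial dates, a reader might infer that the Protocol excludes partially dated events that began in follow-up. The documents do not support that. Protocol 7.2.6 has no partial-date rule, and Protocol 7.3 plans no imputation of safety values. Where the month overlaps the window, counting the event is a reasonable conservative default. Protocol 8.3.1 also makes the onset date mandatory, so incomplete dates should be rare. What stands is the contradiction within the SAP for provably late dates.

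It can also be said that the 4-day sentence was plainly meant to implement the Protocol's REP, and that SAP section 1 falls back on the Protocol unless it says otherwise. That argues for treating this as a wording defect rather than an intended departure. It does not tell a programmer which text to code, because SAP 4.11.1 is explicit.

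**Conclusion.** The point holds, as a minor one. SAP 4.11.1 leaves the worsening of a pre-dose AE open-ended, so it can count an event that Protocol 7.2.6 would not. For partial dates that prove onset after the REP, SAP 4.11.1 conflicts with SAP 4.3.1.3.

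The worsening part assumes that a pre-dose AE stays one record with its original start date. The comparison uses Protocol version 4.0, whereas the SAP cites version 3.0; the amendment entries available for version 4.0 do not mention 7.2.6.

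The documents give no expected number of such events, and it is probably small. Safety analysis is descriptive and untested, and patients with any treatment-emergent event from Day 1 to Day 18 are counted under either rule. Only a patient with no other such event moves an arm's figure, by 2.1 to 2.5 points.

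Two stronger readings are not supported. A reader might infer that the extra events dilute the drug-placebo contrast. Nothing in the documents shows this, and equal additions to both arms leave the absolute difference unchanged. A reader might also infer that early discontinuers are affected most, through a long off-drug follow-up. Protocol 3.1 and SAP 3.1 place their last visit 4 days after the last intake, which leaves essentially no time beyond the REP. Protocol 6.2.3 can be read otherwise, so no figure for them is secure.

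**What to change.** 1. Reword the definition in SAP 4.11.1: *A TEAE is an AE whose onset, or whose worsening in severity after first dose, falls between first dose and 4 days after the last dose.* This removes all 10 days of disagreement in Step 3, and makes explicit that the worsening limit runs to the end of the REP.
2. Check whether the eCRF holds a date of worsening. The minimum contents of the AE listing in SAP 4.11.1 do not include one. If there is none, state that a worsening is recorded as a new AE with its own start date.
3. Add a second exit to the partial-date default: *or that the AE started more than 4 days after the last dose.* State how the default and the imputation in SAP 4.3.1.3 work together. Keep the conservative default where the partial date overlaps the window.
4. List later onsets and worsenings as post-treatment events so that none is lost from the report.

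The cost is a few sentences in the SAP and a small change to the flag. The treatment-emergent count may fall slightly. The main practical constraint is whether a worsening date is available; item 2 covers the case where it is not.
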